1.0 Study Summary

Study Title	Assessment of the accuracy of the manual palpation of surface landmarks versus ultrasound for identification of the correct intervertebral space for spinal anesthesia in children less than 1 year of age.
Study Design	Prospective study
Primary Objective	The primary objective of the study is to compare the accuracy of manual palpation of surface landmarks versus ultrasonography for identification of the appropriate interspace for lumbar puncture and spinal anesthesia in infants less than 1 year of age.
Secondary Objective(s)	The secondary objective is to assess the level of the conus medullaris in infants in the sitting and lateral position.
Research Intervention(s)/ Investigational Agent(s)	Ultrasound
IND/IDE #	N/A
Study Population	Main OR surgical patients
Sample Size	50
Study Duration for individual participants	Less than 30 minutes total.
Study Specific Abbreviations/ Definitions	N/A

2.0 Objectives

- 2.1 The primary objective of the study is to compare the accuracy of manual palpation of surface landmarks versus ultrasonography for identification of the appropriate interspace for lumbar puncture and spinal anesthesia in infants less than 1 year of age.
- 2.2 The secondary objective is to assess the level of the conus medullaris in infants in the lateral position and also in the sitting position.
- 2.3 The hypothesis is that ultrasonography will be more accurate than the traditional method of palpation of surface landmarks in the identification of the appropriate interspace for lumbar puncture and spinal anesthesia in children less than 1 year of age.

3.0 Background

- 3.1 Spinal anesthesia may be used instead of general anesthesia in children for lower abdominal surgical procedures. The conus medullaris ends at L3-L4 in children less than 1 year of age and therefore the L3-4 or L4-5 interspace is

PROTOCOL TITLE: Accuracy of manual palpation vs ultrasound for spinal anesthesia in children less than 1 year of age.

suggested as the optimal site for lumbar puncture for spinal anesthesia. Manual palpation is commonly performed to identify the correct intervertebral space for spinal anesthesia. Studies in adults and children have shown that manual palpation can be inaccurate in up to 30% of cases.¹⁻³ Traumatic needle placement or the administration of a concentrated local anesthetic agent into the spinal cord can lead to serious morbidity including neurologic damage and even paraplegia.^{2,4} Ultrasonography may be used to assess the intervertebral space prior to spinal anesthesia in adults especially in difficult cases and in children to locate the tip of epidural catheter. Introduction of the ultrasound for assessment of the correct intervertebral space for spinal anesthesia may decrease the number of attempts and the possibility the incidence of serious adverse effects.

4.0 Study Endpoints

- 4.1 The accuracy of manual palpation of surface landmarks for identification of the appropriate interspace (L3-4/L4-5) for lumbar puncture and spinal anesthesia.
- 4.2 The level of the conus medullaris lateral and sitting.

5.0 Study Intervention/Investigational Agent

- 5.1 The only intervention being used that is not normally used in general clinical practice is the use of ultrasonography. The technique is non-invasive and poses no risk. Ultrasonography will be performed by an anesthesiologist with training and experience and will add less than 10 minutes to the anesthetic time.

6.0 Procedures Involved*

- 6.1 Anesthetic management will not vary from the standard technique and will be at the discretion of the anesthesia team. The clinical anesthesia provider (fellow or attending) who will be performing spinal anesthesia will mark the interspace for spinal anesthesia with a marking pen. The study team will record the providers years of experience performing spinal anesthesia. The research anesthesiologist performing the ultrasound will confirm whether or not the appropriate interspace (L3-4/L4-5) has been identified. Also, the interspace where the conus medullaris ends will be identified in the sitting position. Spinal anesthesia will be performed at the space confirmed by ultrasound using our standard clinical care.

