17.0 Data Management* and Confidentiality

17.1 A 2 by 2 contingency table with a chi-squared analysis will be performed to compare the accuracy of surface palpation versus ultrasonography. Other data including time to perform ultrasonography and level at which the conus medullaris ends will be presented as secondary outcomes in tabular format for descriptive purposes without the need for statistical comparison or analysis.

17.2 Research records will be stored in a locked cabinet and password protected computer. Only certified research personnel will be given access to identifiable subject information.

17.3 Once the data collection and analysis are complete and the study results have been published identifiers will be destroyed. Six years after research is complete, per NCH guidelines as this meets both HIPAA and OHRP regulations, all electronic files will be permanently deleted.

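### Ultrasound is both a method under test and the only judge of correctness, so the hypothesis that it is more accurate than palpation cannot be tested

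*Combined protocol and SAP*

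**What the plan says.** The primary objective (sections 1.0 and 2.1) is to "compare the accuracy of manual palpation of surface landmarks versus ultrasonography for identification of the appropriate interspace". Section 2.3 gives it a direction: "The hypothesis is that ultrasonography will be more accurate than the traditional method of palpation of surface landmarks". Section 17.1 supplies the only inferential analysis in the protocol: "A 2 by 2 contingency table with a chi-squared analysis will be performed to compare the accuracy of surface palpation versus ultrasonography".

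Section 6.1 describes how correctness is decided. The clinical provider marks an interspace by palpation, and then "The research anesthesiologist performing the ultrasound will confirm whether or not the appropriate interspace (L3-4/L4-5) has been identified". The same section continues: "Spinal anesthesia will be performed at the space confirmed by ultrasound using our standard clinical care".

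The endpoint in section 4.1 is narrower than the objective. It names "The accuracy of manual palpation of surface landmarks for identification of the appropriate interspace (L3-4/L4-5") and has no counterpart for ultrasound. The sample size is 50 (sections 1.0 and 12.1), given without a significance level, power or assumed effect.

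**The concern.** A comparison of two accuracies needs a standard that is independent of both methods. Here the ultrasound reading is one of the two methods and also the standard. Measured against itself, ultrasound cannot be found wrong about the level. An infant in whom palpation was right and ultrasound wrong is recorded as a palpation error.

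The result can therefore favour ultrasound or show no difference, but it cannot favour palpation. A significant p-value would very likely be published as evidence that ultrasound is more accurate, although the data contain nothing about ultrasound's own error rate. That is the study's primary conclusion.

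**Working it through.** **Where the two rows of the 2 by 2 table come from**

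- Palpation row: right or wrong according to the ultrasound reading (6.1).
- Ultrasound row: no source is defined. The documents describe no other imaging, second reader or external standard. Because the spinal is placed at the space that ultrasound confirmed, the puncture is no separate check of level. If every scan is readable, the row can only be 50 right, 0 wrong.

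**When the test becomes significant**

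Inputs: n = 50 (12.1); two-sided 5% level (assumed, since the plan gives none). Let k be the number of infants in whom the two methods disagree. The table is (50 − k, k) against (50, 0), and the statistics reduce to:

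- uncorrected: χ² = 100k / (100 − k)
- Yates: χ² = 100(k − 1)² / [k(100 − k)]

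| k | Uncorrected χ² (p) | Yates χ² (p) |
|---|---|---|
| 3 | 3.09 (0.079) | 1.38 (0.241) |
| 4 | 4.17 (0.041) | 2.34 (0.126) |
| 5 | 5.26 (0.022) | 3.37 (0.067) |
| 6 | 6.38 (0.012) | 4.43 (0.035) |

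The threshold is 4 disagreements uncorrected and 6 with Yates. Section 17.1 does not say which form will be used.

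Section 3.1 says that "manual palpation can be inaccurate in up to 30% of cases". At 30%, the expected table is 35/15 against 50/0, and χ² = 1500/85 = 17.6, p = 0.00003. This figure is the same whatever the true accuracy of ultrasound.

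**How often ultrasound is declared superior**

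The documents give no ultrasound error rate, so the rates below are assumptions. Let palpation truly err in a fraction e_P of infants. Let ultrasound give the wrong yes/no verdict in a fraction e_U, independently of palpation and at the same rate for correct and incorrect marks. The apparent palpation error is

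q = e_P(1 − e_U) + e_U(1 − e_P),

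and the chance of significance is P(K ≥ 4) or P(K ≥ 6) with K ~ Binomial(50, q).

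| True error, palpation / ultrasound | Apparent palpation error q | Uncorrected | Yates |
|---|---|---|---|
| 2% / 2% | 3.92% | 13% | 1.3% |
| 5% / 5% | 9.5% | 71% | 34% |
| 10% / 10% | 18% | 98.6% | 90.7% |
| 5% / 10% (palpation better) | 14% | 93% | 72% |
| 0% / 10% (palpation perfect) | 10% | 75% | 38% |

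In the first three rows the methods are equally accurate, so a valid test would reject in about 5% of studies. In the last two rows the declared conclusion is the reverse of the truth.

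**Would a paired test cure it?**

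Each infant is assessed by both methods, so an ordinary chi-squared test also ignores the pairing. McNemar's test would respect it, but one discordant cell (palpation right, ultrasound wrong) is zero by design. Its exact two-sided p-value is 2 × 0.5^k, below 0.05 from k = 6 (0.031). The direction is still fixed in advance.

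**The case against.** The strongest reply is that ultrasound is simply the reference standard. Section 4.1 lists only palpation accuracy, section 6.1 uses ultrasound to judge the palpated mark, and the planned data answer that question without change. On this view the fault is loose wording in 2.1, 2.3 and 17.1. It is true that the study remains informative. But those sections hold the primary objective, the hypothesis and the only planned test, and a reference standard cannot also be a comparator hypothesised to be superior.

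Three narrower points stand in part:

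- The protocol never sets out the table cells or says how an unreadable scan is scored, so 50/0 is an inference. The exact statement is that no ultrasound error of level can be detected. The direction of the bias is the same.
- The probabilities are illustrative. The target covers two interspaces, so an ultrasound reading that is one level out need not change the verdict, and positively correlated errors would lower the apparent palpation error. Across the equal-error rows shown, the probability runs from about 1% to 99%. The structural argument needs none of these figures.
- The hypothesis could instead be kept by adding an independent reference and a paired analysis. That is a valid but larger change, and the documents give no ultrasound accuracy or discordance rate from which to size it.

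**Conclusion.** The concern holds. As written, the primary comparison cannot test the hypothesis in 2.3, because the ultrasound reading defines what is correct. This follows from sections 2.1, 2.3, 6.1 and 17.1 alone.

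The size of the false claim depends on assumed error rates, independent errors and a two-sided 5% level. With equal true error of 10%, ultrasound is declared superior in 98.6% of studies (90.7% with Yates); with 5%, in 71% (34%); with 2%, in 13% (1.3%). The data can support an estimate of how often palpation agrees with ultrasound. This must be fixed before the analysis, since the plan followed as it stands would report an invalid superiority conclusion.

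**What to change.** - **Sections 1.0, 2.1 and 2.3:** restate the primary aim as estimating the accuracy of palpation with ultrasound as the reference standard, and delete the superiority hypothesis. Bring the study title into line.
- **Section 17.1:** delete the chi-squared comparison. Report the proportion of infants whose palpated mark is at L3-4/L4-5 according to ultrasound, with an exact (Clopper-Pearson) 95% confidence interval. State that no conclusion on the accuracy of ultrasound will be drawn.
- **Ultrasound itself:** report feasibility only, as the proportion of infants in whom the level could be determined and the scan time. State how infants with an unreadable scan enter the palpation proportion.

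The cost is wording, plus one data field for whether the level could be determined; scan time is already planned in 17.1. No extra infants, staff or procedures are needed. The price is a more modest claim: 15 wrong marks in 50 would be reported as 30% wrong (95% CI 17.9% to 44.6%), or equivalently 70% correct (55.4% to 82.1%).

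If the sponsor prefers to keep the comparison, the protocol needs a reference standard independent of both methods, a paired analysis and a new sample-size justification.

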25.0 Resources Available

25.1 The department of Anesthesiology and Pain Medicine has 2 research coordinators and 2 research associates that will be enrolling subjects for this study. All study staff will be trained on the study procedures.

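### Section 6.1 does not require the ultrasound level call that scores endpoint 4.1 to be fixed before the palpation mark is consulted

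*Combined protocol and SAP*

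**What the plan says.** Endpoint 4.1 is "The accuracy of manual palpation of surface landmarks for identification of the appropriate interspace (L3-4/L4-5) for lumbar puncture and spinal anesthesia". Section 6.1 describes how it is obtained. First, "The clinical anesthesia provider (fellow or attending) who will be performing spinal anesthesia will mark the interspace for spinal anesthesia with a marking pen". Then, "The research anesthesiologist performing the ultrasound will confirm whether or not the appropriate interspace (L3-4/L4-5) has been identified". The same section has the operator identify where the conus ends, and 17.1 tabulates that level. It closes with "Spinal anesthesia will be performed at the space confirmed by ultrasound using our standard clinical care".

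On the operator, 5.1 says "Ultrasonography will be performed by an anesthesiologist with training and experience and will add less than 10 minutes to the anesthetic time". On staff, 25.1 says "All study staff will be trained on the study procedures". On analysis, 17.1 says "A 2 by 2 contingency table with a chi-squared analysis will be performed to compare the accuracy of surface palpation versus ultrasonography". None of these passages sets an order between counting the levels and looking at the mark, keeps the mark out of view, or provides a second or stored-image reading.

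**The concern.** When one method is scored against another, the reference call should not depend on the result it judges. Here the reference call is worded as a confirmation of an ink mark on the skin. An operator who counts levels first complies with 6.1, and so does one who starts at the mark and asks whether it looks right.

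Two opposite pulls are plausible. An operator anchored on the mark may confirm too readily. An operator who expects ultrasound to do better, as hypothesis 2.3 does, may reject too readily. No other reading feeds endpoint 4.1, so a net pull would pass straight into the reported accuracy of palpation. Enrolling more infants would narrow the confidence interval but would not remove the bias. The order of reading cannot be reconstructed after the scan unless it was recorded.

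**Working it through.** **Provisions that could protect the reading**

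| Section | Provision | Effect on independence |
|---|---|---|
| 6.1 | Palpation by the clinical provider, scan by a research anesthesiologist | Separate operators; no masking |
| 5.1 | Trained, experienced operator | Fewer misreadings; order not set |
| 6.1, 17.1 | Conus level identified and tabulated | One named level per infant, so a partial check; not required before the mark is consulted, and does not name the marked interspace |
| 6.1 | Spinal placed where ultrasound confirms | An incentive to read carefully; not masking |
| 25.1 | General staff training | Order of reading not mentioned |
| 18.1 | Monitoring by the study investigators only | No independent reading |

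The protection is partial. What is missing is a fixed level call before comparison.

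**Size, as illustration only.** The plan gives no figure for misreading, so there is none to reproduce. The inputs are:

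- *n* = 50 (12.1).
- *p*, the true palpation error. Section 3.1 says "Studies in adults and children have shown that manual palpation can be inaccurate in up to 30% of cases", so 30% is taken as an upper value, with 20% and 10% as assumed lower ones.
- *a*, the share of wrong marks confirmed, and *b*, the share of correct marks rejected. Both are assumed. Only misreadings across the edge of the L3-4/L4-5 window count, because confusing those two interspaces leaves the score unchanged.

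Scored error = p(1 − a) + (1 − p)b. For example, with p = 0.30, a = 0.10 and b = 0.05: 0.30 × 0.90 + 0.70 × 0.05 = 0.270 + 0.035 = 0.305.

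| True error p | a = 10% only | b = 5% only | Both | Exact 95% interval at n = 50 |
|---|---|---|---|---|
| 30% (15/50) | 27% | 33.5% | 30.5% | 17.9% to 44.6% |
| 20% (10/50) | 18% | 24% | 22% | 10.0% to 33.7% |
| 10% (5/50) | 9% | 14.5% | 13.5% | 3.3% to 21.8% |

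The largest shift here is at p = 10% with b = 5%: 0.90 × 0.05 × 50 = 2.25 infants. Every entry lies inside its interval.

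The two errors cancel when b = a·p/(1 − p). For a = 10% this gives 0.03/0.70 = 4.3%, 0.02/0.80 = 2.5% and 0.01/0.90 = 1.1% at p = 30%, 20% and 10%. The sign of the net bias therefore turns on quantities that the documents do not give.

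Because *a* and *b* are guesses, a wider range is needed:

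- With *a* alone at p = 30%, a = 20%, 30% or 50% scores 0.30 × (1 − a) = 24%, 21% or 15%. Only the last falls below 17.9%.
- With *b* alone at 10%, p + (1 − p) × 0.10 gives 37%, 28% and 19% at p = 30%, 20% and 10%, all inside their intervals.
- With *b* alone at 20%, the results are 44%, 36% and 28%. The last two lie above their upper limits of 33.7% and 21.8%.

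Modest misreading is hard to tell from sampling error at 50 infants. Only high assumed rates move the estimate outside the interval, and the documents neither support nor exclude such rates.

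**The case against.** The strongest reply is that this is a silence in the text with no demonstrated effect. The operator is trained and did not palpate. The reading guides where the needle goes, which is a reason not to wave a mark through. The operator also reports a conus level, so the record is not a bare yes/no. The window is two interspaces wide, and the two pulls may offset each other. All of this stands, and it limits the weight of the point.

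It does not close the gap. Separate operators are not masked operators, and skill does not decide whether the levels are counted before or after looking at the mark.

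A reader might infer that the operator does see the mark first and is biased by it. The documents do not say so: 6.1 is compatible with counting levels first, and independence is unprotected rather than shown to be absent. Nor is seeing the mark a fault in itself, since it must be compared with a level at some point. A reader might also infer that the confirmation wording inflates palpation accuracy, or that the hypothesis deflates it. The text supports neither direction over the other.

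A further objection concerns remedies. Compulsory covering, or having staff match skin marks without a re-scan, could obstruct the probe or add alignment error at the window edge, exactly where the score is decided. That objection is sound, and the change proposed here avoids both.

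**Conclusion.** The point holds in a limited form. Endpoint 4.1 rests on one reading, and no passage requires that reading to be fixed before the palpation mark is consulted. Recording the levels first is less open to bias than confirming a mark already on the skin, and it needs no extra staff, so 6.1 should be amended.

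The direction and size of any net bias are unknown from the documents and are not shown to be large. Under the smaller assumed rates, the shift is at most 2.25 infants in 50. That figure depends wholly on assumed misreading rates and on 30% as an upper value for palpation error. The stronger conclusion, that the palpation result would be invalid or materially biased, is not supported.

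**What to change.** Amend 6.1 to set the order of reading:

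1. The ultrasound operator counts levels from a fixed landmark named in the protocol, without reference to the palpation mark, which is kept out of view where practicable.
2. The operator marks L3-4 and L4-5 and records them by name.
3. Only then does the same operator compare the palpation mark with those levels and record the named interspace it lies over. Yes/no for L3-4/L4-5 is derived from that record.

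Re-scanning need not be barred, and covering need not be compulsory. Named interspaces would also show whether a wrong mark was too high or too low.

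The cost is a short added recording step per infant. The documents give no time for it, and it must fit within the limit of under 10 minutes in 5.1. Masking stays incomplete where the mark cannot be hidden. The clinical management described in 6.1 is unchanged. The change does not resolve the separate problem that ultrasound is both comparator and reference in the comparison planned in 17.1.

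### Section 6.1 has no category for a conus tip opposite a vertebral body, so such a tip must be rounded to an interspace, by up to half a segment or more

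*Combined protocol and SAP*

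**What the plan says.** The secondary objective in Section 2.2 is to "assess the level of the conus medullaris in infants in the lateral position and also in the sitting position". Section 4.2 lists the matching endpoint as "The level of the conus medullaris lateral and sitting". Neither gives a unit or a resolution.

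The only operational text is in Section 6.1: "the interspace where the conus medullaris ends will be identified in the sitting position". It names the interspace as the recording unit and describes a sitting reading only. It does not say what to record when the tip lies opposite a vertebral body.

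Under Section 17.1 the conus level, with other data, "will be presented as secondary outcomes in tabular format for descriptive purposes without the need for statistical comparison or analysis". The Background (3.1) states its premise in the same kind of label: "The conus medullaris ends at L3-L4 in children less than 1 year of age". The target for the primary endpoint is L3-4 or L4-5 (4.1 and 6.1). The planned size is 50 infants.

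**The concern.** A conus tip can end opposite a vertebral body as well as at an interspace. An operator who follows 6.1 literally has one category per segment and must move a body-level tip up or down to the neighbouring space, with no rule for which.

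The Background places the conus at the upper edge of the target window, so the rounding falls where it matters most for interpretation. A mid-L3 tip recorded as L2-3 lies above the window. The same tip recorded as L3-4 lies inside it. The table would then mix anatomy with operator habit. Because the table is the whole planned analysis of this outcome, nothing later would separate the two.

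The same coarse step limits what can be seen between positions: a movement smaller than a segment shows only if it happens to cross a category boundary.

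**Working it through.** **Inputs from the documents.** Recording unit: interspace (6.1). Positions: sitting in 6.1; lateral and sitting in 2.2 and 4.2. N = 50 (Study Summary, 12.1). The plan gives no figure for resolution, expected shift or spread, so there is nothing of its own to reproduce.

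**Assumptions.** Position is measured in segments, from one interspace centre to the next. Tips are uniform within a segment unless stated. The vertebral body takes a share b of segment height, with b = 0.6 to 0.8; this range is not in the documents.

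**1. Rounding error.**
- Nearest interspace: the worst case is mid-body, error 0.5 segment. With uniform tips the mean absolute error is 0.25 and the SD is 1/√12 = 0.289.
- Always one way: a tip at the far edge of a body is b + (1 − b)/2 = (1 + b)/2 from the interspace chosen, so 0.8 segment for b = 0.6 and 0.9 for b = 0.8.
- Share of tips opposite a body equals b: 0.6 × 50 = 30 to 0.8 × 50 = 40 infants. This follows wholly from the assumed b.

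**2. Chance that a shift changes the recorded interspace.** For uniform tips and a shift s between 0 and 1 segment, P(change) = s. A simulation of 1,000,000 draws agreed.

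| Shift (segments) | Category changes | Recorded as unchanged |
|---|---|---|
| 0.10 | 10% | 90% |
| 0.25 | 25% | 75% |
| 0.50 | 50% | 50% |
| 0.75 | 75% | 25% |
| 0.90 | 90% | 10% |

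Averaged over a spread of shifts, the share that shows is 50% for shifts even over 0 to 1 segment, 25% over 0 to 0.5, 75% over 0.5 to 1, and about 24% for a half-normal shift with scale 0.3.

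**3. Group mean.** With uniform tips, the mean recorded shift equals the true shift. For s = 0.25 it is 0.25, with SE √(0.25 × 0.75/50) = 0.061 in 50 paired infants. About 0.25 × 50 = 12.5 infants would move one category.

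**4. Tips not uniform, s = 0.25.** A change is recorded in 0.6% (tip SD 0.1) or 10.5% (SD 0.2) of infants when tips cluster at an interspace centre, and in 49% or 39% when they cluster at mid-body. Each infant moves at most one step, so the mean recorded shift is about 0.01, 0.11, 0.49 and 0.39, against a true 0.25.

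**5. Finer scales, s = 0.25, uniform tips.**
- Body or interspace: for b = 0.6, unchanged = (0.6 − 0.25) + (0.4 − 0.25) = 0.50, so 50% change. For b = 0.8, unchanged = 0.8 − 0.25 = 0.55, so 45% change. The largest error from the category centre is b/2 = 0.3 to 0.4.
- Body thirds or interspace: for b = 0.6 the thirds are 0.20 wide, so unchanged = 0.4 − 0.25 = 0.15 and 85% change. For b = 0.8 the thirds are 0.267 wide, so unchanged = 3 × (0.267 − 0.25) = 0.05 and 95% change. The largest error is 0.20 or 0.13.

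**The case against.** **The interspace is a natural unit here.** The primary endpoint is defined by interspaces and the Background uses the same label. That is a fair reason to report interspaces. It does not tell the operator what to write for a tip that is not at one, and a finer record can still be collapsed.

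**A finer record is not ruled out.** Sections 2.2, 4.2 and 17.1 say level, and no data collection form is among the documents. This stands: the protocol does not forbid finer recording, but nothing in it asks for any.

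**Shift is not an endpoint.** The plan asks for the level in each position, shown descriptively, and defines no difference between them. Moreover, 6.1 describes no lateral reading, so as written no shift of any size could be seen on any scale. Both stand, and they limit the weight of the shift argument.

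**Stronger readings.** A reader might infer that most shifts smaller than one segment would go unseen. That does not follow: the chance of showing equals the size of the shift, so about half show if shifts are spread evenly over 0 to 1 segment, and the documents give no shift size. A reader might also infer that the table would falsely suggest a stable conus. With uniform tips the group mean is preserved (step 3). It can be distorted in either direction if tips cluster (step 4), but the documents give no distribution, and 17.1 plans no mean shift.

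**Thirds may not be readable.** Nothing in the documents shows that thirds of an infant vertebral body can be told apart reliably. This stands, and it is why the fix falls back on body only.

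**Conclusion.** The point holds as a gap in how a secondary outcome is recorded. As 6.1 reads, a tip opposite a vertebral body has no category and is rounded by up to 0.5 segment to the nearest interspace, or by more under a one-way habit. That choice can decide whether a mid-L3 tip appears inside the target window.

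If both positions are read, an individual shift under about half a segment will more often than not be missed. This rests on tips uniform within a segment. In the clustered cases tried, a 0.25-segment shift was also recorded in fewer than half of infants (0.6% to 49%). The figure of 30 to 40 infants needing rounding depends on an assumed body height and is not evidence about this trial.

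The effect is confined to a descriptive secondary table; the primary comparison is untouched. Severity: minor. The absence of a lateral reading in 6.1 is the larger problem at the same place and has to be settled before any question of shift arises.

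**What to change.** - **Section 6.1:** record the conus tip as the named vertebral body (upper, middle or lower third where it can be read, otherwise body only) or the named interspace. Use the same scale in each position.
- **Sections 6.1, 2.2 and 4.2:** reconcile the sitting-only procedure with the objective and endpoint, which name lateral and sitting.
- **Section 17.1:** tabulate on the finer scale, with a collapse to interspaces by a stated rule if wanted.

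The scale change costs one data field on the same scan, with no added procedure or staff. The downside is a few more categories in a small table and some possible misclassification between adjacent thirds. It should be made before data are collected: 6.1 does not mention keeping images, so rounded readings may not be recoverable later.
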